5.6 Study Discontinuation (Interventional)

The NIH and local IRBs (at their local site) have the authority to stop or suspend this trial at any time. This study may be suspended or closed if:

- Early stopping rules have been met (defined below)
- Accrual has been met
- The study objectives have been met
- The Study Chair / Study Investigators believe it is not safe for the study to continue
- The NIH suspends or closes the trial
- The FDA suspends or closes the trial

5.7 Subject Discontinuation

All data acquired prior to termination for the reasons outlined below will be included in the primary analysis unless patient withdraws consent. Every effort will be made to conduct a final study visit with the participant and participants will be followed clinically until, if applicable, all adverse events resolve.

- Withdrawal of consent
- Withdrawal by the participant
- Withdrawal by the investigator
- Intercurrent illness or event that precludes further visits to the study site or ability to evaluate disease (for example, mental status change, large pleural effusion, large stroke).

Early Stopping Rules: If a participant experiences a significant decline in his or her health or wellbeing, the PIs may remove the participant from the pilot study. This decision will be promptly made on a case-by-case basis with careful discussion between the PIs, the parents and/or patient, and in consultation with the IRB. In some cases, it can be more medically destabilizing to remove the subject from the study drug. However, in any case where a significant decline in health may be attributable to the study drug, or in any case where it is determined that it may not be in the subject's best interest to remain on the study drug, then they will be removed from the study. A significant decline in health or wellbeing could include a loss of seizure control and/or the occurrence of intolerable side effects. Loss of seizure control is defined as an increase in seizure frequency and/or severity or use of emergency medications that warrant the initiation of a new seizure medication or treatment such as, Ketogenic/Atkins diet, surgery, or VNS. If there has been a loss of seizure control, then the subject will be removed from the study drug at that time, he or she will complete the ending assessments, and then the subject will be removed from the trial. Other stopping criteria are listed in Tables 1 and 2 above. Other removal criteria include: death, lost to follow-up, withdrawal of consent for any further data submission, or inability to complete follow up two years from the protocol completion. Early withdrawals within the first two months on the study drug will be replaced with a new study subject.

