of warfarin or on a stable dose of LMW heparin for >2 weeks.)
of warfarin or on a stable dose of LMW heparin for >2 weeks.) 9. Adequate liver function as shown by:
of warfarin or on a stable dose of LMW heparin for >2 weeks.)

- 10. Written informed consent according to local guidelines. Local guidelines for subject assent will also be followed.
 11. Stable dose of medications affecting the cytochrome P 450 3A4 (CYP3A4) and p glycoprotein (P gp) systems for at least 3 months prior to consent.

Treatment				
Agent-	Rapamune® / Rapamycin® (sirolimus)			
Dosage,	Oral dose targeting a serum level dose range of 4-6 ng/mL given for a minimum of			
schedule, route of	six months. Dose based on surface age, surface area, and mini-PK as outlined in			
administration-	the protocol.			
	Subjects will receive no more than 2 mg/day given in two divided doses for a			
1	minimum of six months with the option to enter into the Extension Phase up to an			
	additional year and a half.			
Primary	Safety and Tolerability of sirolimus in patients with Sturge-Weber syndrome.			
Outcome	Adverse Events will be determined at every visit and on every phone call			
Measures:	using a case report with a list of side effects which can be seen with higher			
	doses and serum levels than are expected with this study. Impact of the			
	study drug upon seizure frequency, type, and duration will be assessed by			
	patient/parent report using a seizure report form we have used in a prior study. Impact of study drug upon neurologic, ophthalmologic, endocrine,			
	medical rehab, and dermatologic status will be assessed with case report			
	forms, the physical exam, the Sturge-Weber syndrome neuroscore, the port-			
	wine birthmark score, and other outcome measures described in the			
	protocol.			
	Change over six months in cognitive functioning in Sturge-Weber syndrome			
	is the primary outcome measure. This outcome will be assessed using a			
	panel of testing selected based upon extensive experience in testing			
	cognitive function in adults and children with SWS at the Kennedy Krieger			
	Sturge-Weber Center. These will include the following measures from the			
	National Institute of Health Toolbox (Gershon et al., 2010):			
	Attention/Executive Function – Flanker Inhibitory Control and Attention Test (Eriksen & Eriksen, 1974)			
	Executive Functioning – Dimensional Change Card Sort Test (Zelazo, Frye, & Rapus,1996)			

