Serious toxicities are not expected with the low dose range being used for this pilot study. Any patient experiencing a Grade 3 or 4 toxicity that is possibly, probably, or definitely related to sirolimus will have the drug held and a sirolimus trough level obtained as soon as possible. Other toxicities requiring dose adjustments will be defined based on categorization of toxicity and sirolimus trough levels.

Hematological Toxicity - If a patient experiences ≥Grade 3 neutropenia (ANC <750), anemia (Hgb <8), the sirolimus will be withheld and the subject will be removed from the study. Patients will continue to be seen, treated as needed, and have complete blood counts measured. In addition, sirolimus trough levels will be obtained every week until recovery (≤Grade 1) is documented.

Non-Hematological Toxicity - For toxicities attributable (possibly, probably, definitely) to sirolimus:

If a patient experiences a non-hematological toxicity as defined below, sirolimus will be withheld and the subject will be removed from the pilot study. Patients should continue to be seen and have appropriate labs/observations. In addition sirolimus trough levels will be obtained at every visit until recovery (≤Grade 1) is documented.

Sirolimus-related (possibly, probably, or definitely) toxicities Requiring Dose Interruptions or other interventions and removal from study:

- Grade 3 or Grade 4 non-hematological toxicity (*)
- Grade >2 serum creatinine elevation
- Grade ≥2 allergic reaction
- Grade ≥2 hypertension
- Grade ≥1 non-hematologic toxicities related to sirolimus that are intolerable to the patient
- Any ≥ Grade 2 non-hematological toxicity that persists for ≥ seven days without resolution (return to less than Grade 2 or baseline) and is considered sufficiently medically significant or sufficiently intolerable by patients that it requires treatment interruption
- (*) The only non-hematological toxicities that are excluded from requiring dose adjustments/interruptions or other interventions are the following:
 - Grade 3 nausea and vomiting of less than three days duration
 - Grade 3 transaminase elevations that return to levels that meet initial eligibility criteria within seven days of study drug interruption and that do not recur upon study re-challenge with study drug
 - Grade 3 GGT elevation
 - Grade 3 lymphopenia

Interventions for Hyperlipidemia/Hypertriglyceridemia

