study drug and at the end of the study while still on the study drug. An asymmetry in power (roughly an integration of amplitude and frequency) in the affected side of the brain compared to the unaffected (or less affected) side of the brain, will be quantified as previously described (Hatfield et al., 2007; Ewen et al., 2009) for the quantitative EEG analysis. EEGs will occur at both sites, KKI and CCHMC, and the de-identified EEGs will be sent to KKI for analysis. The reason for this analysis is as a non-invasive biomarker of brain function which could be useful to develop as a marker of drug response. Quantitative EEG power analysis reflects an integration of the EEG activity amplitude and frequency. Therefore asymmetry of power on gEEG for these subjects reflects the increased slowing and decreased amplitude frequently seen in these patients interictally as their neurologic involvement progresses. Even patients with bilateral brain involvement have more involvement on one side than on the other side. Power asymmetry on gEEG has been shown to correlate with brain perfusion, brain atrophy, and SWS neuroscore, therefore, it has the potential as a biomarker responsive to monitor sirolimus treatment, both from the standpoint of safety and efficacy in a future larger clinical trial.

 Neuropsychological testing will be done at baseline and after six months on study drug.

Change over six months in cognitive functioning in Sturge-Weber syndrome is the primary outcome measure. This outcome will be assessed using a panel of testing selected based upon extensive experience in testing cognitive function in adults and children with SWS at the Kennedy Krieger Sturge-Weber Center. These will include the following measures from the National Institute of Health Toolbox (Gershon et al., 2010):

Attention/Executive Function – Flanker Inhibitory Control and Attention Test (Eriksen & Eriksen, 1974)

Executive Functioning – Dimensional Change Card Sort Test (Zelazo, Frye, & Rapus, 1996)

Episodic Memory – Picture Sequence Memory Test (Bauer et al., 2013; Dikmen et al., 2014)

Language – Oral Reading Recognition Test

Language - Picture Vocabulary Test (Dunn & Dunn, 1981)

Processing Speed – Pattern Comparison Processing Speed Test (Carlozzi et al., 2014)

Working Memory – List Sorting Working Memory Test (Weintraub et al., 2013)

Dexterity – 9-hole Pegboard Dexterity Test (Wang, Bohannon, Kapellusch, Garg, & Gershon, 2015)

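### Section 5.7, read literally, drops from the primary analysis all data already collected on a subject who formally withdraws consent, adverse events included, and it contradicts itself on this point

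*Combined protocol and SAP*

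**What the plan says.** Section 5.7 (Subject Discontinuation) sets the rule for subjects who leave: "All data acquired prior to termination for the reasons outlined below will be included in the primary analysis unless patient withdraws consent". Four reasons follow as bullets. The first is withdrawal of consent itself. The second and third are "Withdrawal by the participant" and "Withdrawal by the investigator". The fourth is an intercurrent illness or event.

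Further down, the paragraph on early stopping rules names other removal criteria, one of which is "withdrawal of consent for any further data submission". It also says that subjects who leave within the first two months on drug are replaced. The Synopsis does not count those subjects in the sample size of 10.

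The Synopsis (Primary Outcome Measures) opens with "Safety and Tolerability of sirolimus in patients with Sturge-Weber syndrome". It then adds cognition, in words repeated in section 5.3: "Change over six months in cognitive functioning in Sturge-Weber syndrome is the primary outcome measure". Neither section 5.7 nor section 6 (Statistical Considerations) defines a safety analysis set.

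**The concern.** The exception covers all data and makes no allowance for safety data. Whether a subject's adverse events count therefore depends on how that subject left. If poor tolerance makes formal withdrawal of consent more likely, the exclusion is related to the outcome and adverse event rates are biased downward. The Synopsis uses these results to judge whether the drug is well enough tolerated to justify a larger trial.

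The rule is also hard to apply consistently. When a family says it wants to stop, one site may record withdrawal of consent and the other withdrawal by the participant. The first record removes the subject's data and the second keeps them. The protocol gives neither site a way to choose.

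**Working it through.** The point rests on wording, and the plan has no figure to reproduce: section 6 justifies the sample size of 10 by availability and experience, without a calculation.

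**Step 1. Is the rule consistent?** Three statements in section 5.7 bear on data collected before consent is withdrawn.

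- The closing clause of the rule: excluded.
- The bullet list the rule points to, whose first entry is withdrawal of consent: included.
- The later removal criterion, "withdrawal of consent for any further data submission": only future data are affected, so earlier data would stay.

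The first cannot be reconciled with the other two. The first is the explicit exception, so an analyst following the text literally would exclude.

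**Step 2. Who is exposed?** The routes out of the trial, and what happens to the data:

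- Removal for toxicity (section 5.3), including "Grade ≥1 non-hematologic toxicities related to sirolimus that are intolerable to the patient": not withdrawal of consent, so data kept.
- Removal by the investigators for a decline in health (section 5.7): "A significant decline in health or wellbeing could include a loss of seizure control and/or the occurrence of intolerable side effects". Data kept.
- Stopping when a subject is not doing well and the patient, parent or investigator thinks it best (section 7): described as removal from the study, so data kept.
- "Withdrawal by the participant" without withdrawal of consent: data kept.
- Formal withdrawal of consent: data excluded on the literal reading.

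Only the last route is exposed, together with any departure that a site records that way.

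**Step 3. What could one exclusion do?** The documents give no rate of consent withdrawal, so the counts below are assumptions. Intervals are exact (Clopper-Pearson) 95% intervals. For 0 of n the upper limit is 1 − 0.025^(1/n). For 1 of n the lower limit is 1 − 0.975^(1/n), and the upper limit solves (1 − p)^n + n·p·(1 − p)^(n−1) = 0.025.

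| Assumed case | Data kept | Data dropped |
|---|---|---|
| One related serious adverse event, in a consent withdrawer | 1/10 = 10% (0.3% to 44.5%) | 0/9 = 0% (0% to 33.6%) |
| Same, but the subject leaves in the first two months and is replaced | 1/11 = 9.1% (0.2% to 41.3%) | 0/10 = 0% (0% to 30.9%) |
| Two subjects intolerant, one a consent withdrawer | 2/10 = 20% (2.5% to 55.6%) | 1/9 = 11% (0.3% to 48%) |
| Two subjects intolerant, both consent withdrawers (extreme case) | 2/10 = 20% (2.5% to 55.6%) | 0/8 = 0% (0% to 36.9%) |

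For 0/9 the upper limit is 1 − 0.025^(1/9) = 0.336. For 1/10 the lower limit is 1 − 0.975^(1/10) = 0.0025.

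**Step 4. Adverse event rate.** Section 5.0 expects about 0.7 events per subject per month. Assume nine subjects at that rate for six months: 9 × 6 × 0.7 = 37.8 events in 54 subject-months. Assume the tenth withdraws consent at month 3.

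- At 1.4 events per month the tenth subject adds 3 × 1.4 = 4.2 events. Kept: 42.0/57 = 0.74.
- At 2.8 events per month the tenth subject adds 3 × 2.8 = 8.4 events. Kept: 46.2/57 = 0.81.
- Dropped: 37.8/54 = 0.70 in both cases.

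The pooled rate moves modestly. Counts of rare serious events are the more sensitive measure.

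**The case against.** A reader might infer that the adverse events of everyone who quits because of side effects leave the primary result. The documents do not support that: the routes in step 2 cover most such departures without touching the exception.

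Reported events are not lost either. Under sections 5.4 and 5.5, serious events are reported within 24 hours or 5 working days, and an NIH-appointed Medical Review Officer determines causality. The adverse event system keeps the record, and aggregate reports cover all reported events with no exception for withdrawn consent. A reader might also infer that the trial could end up reporting no intolerance at all. That needs every intolerant subject to withdraw consent formally, and it ignores these reports.

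Nor do the documents show that the decision on a follow-up trial would be reversed. Section 6 asks for no serious event probably or possibly due to the drug, plus a trend in cognition. It does not tie that to the primary analysis of section 5.7, and the study team would already know of such an event. The Synopsis sets no numerical threshold for tolerability.

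These arguments stand and narrow the point. They do not remove it. Section 5.7 still governs the primary analysis, and its literal result can disagree with the aggregate reports, with no rule for which set of figures informs the tolerability judgement. The consent form, which may say what happens to data already collected, was not available for this check.

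**Conclusion.** The concern holds in limited form. Section 5.7 contradicts itself on data collected before consent is withdrawn, and its explicit exception removes those data from the primary safety and tolerability analysis. Only formal consent withdrawers, and subjects recorded as such, are exposed.

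How often this would happen cannot be read from the documents. In the single-event illustration, a rate of 10% with an upper limit of 44.5% becomes zero with an upper limit of 33.6%. That the bias runs downward assumes that poor tolerance makes withdrawal of consent more likely, which is plausible but not stated in the protocol.

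The effect on the cognitive outcome is small. Testing is planned only at baseline and after six months, so a subject who withdraws consent earlier without a final test has no change score to keep or lose. This should be fixed, but it does not by itself undermine the trial.

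**What to change.** In section 5.7:

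- Delete the exception at the end of the data-retention sentence.
- State that withdrawal of consent ends further collection only. All data collected up to that date, including every adverse event and the reason for leaving, stay in the primary safety analysis, and in the cognitive analysis where a post-baseline test exists.
- Merge the bullets for consent withdrawal and participant withdrawal, or define both and handle their data identically.

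In section 6, define the safety analysis set as every subject who took at least one dose, including early withdrawals who are replaced.

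The cost is a sentence or two in the protocol and, if needed, a matching line in the consent form. No extra subjects or assessments are required. The reported safety rates may look slightly less favourable.

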5.8 Data Quality and Monitoring Measures

As much as possible data quality is assessed at the data entry point using intelligent online data entry via visual basic designed screen forms. Data element constraints, whether independent range and/or format limitations or 'relative' referential integrity limitations, can be enforced by all methods employed for data input. QA reports assess data quality post-data entry. As we note, data quality begins with the design of the data collection forms and procedures and incorporates reasonable checks to minimize transcription and omission errors. Of the more important quality assurance measures are the internal validity checks for reasonableness and consistency.

- Data Monitoring: The RDCRN DMCC identifies missing or unclear data and generates a data query to the consortium administrator contact.
- Data Delinquency Tracking: The Data Management and Coordinating Center will monitor data delinquency on an ongoing basis.

5.9 Quality Control: Study Related Procedures

- 1. Clinical coordinators at both sites will review the case report forms after completion by [name] or [name] to resolve any issues.
- 2. [name] and [name] will review the study progress regularly with monthly phone conferences. The two sites will have internal reviews performed regularly to ensure high quality of the study procedures and subsequent data.
- 3. The DMCC will perform an audit of the overall protocol including this pilot project.

6. Statistical Considerations

The proposed trial is a pilot drug trial. Based on the results, a sample size calculation will be done, using the cognitive outcome with the greatest response to the study drug, to plan a follow up randomized, placebo-controlled trial, should one be warranted. If no serious adverse events which are thought to probably or possibly be due to the study drug AND the cognitive data suggests a trend for possible benefit, then the results of this study will be used to plan a larger follow-up clinical trial.

Children and adults between 3 and 31 years of age with Sturge-Weber syndrome brain involvement and cognitive impairments will be eligible for this pilot study. A total of 10 patients will be enrolled at two centers including Cincinnati Children's Hospital Medical Center and the Kennedy Krieger Institute. This sample size was selected based on 1) availability of potential appropriate subjects at both centers and 2) upon the investigators experience with similar clinical trials.

Cognitive tests proposed have been previously validated in the literature and are normed to aged matched normal controls. These are published tests which are widely used. Therefore, responders in this trial will be subjects whose normed results improve on the task more than what is expected for the increase in age (6 months) +/- expected standard deviation.

Anticipated number of patients to be enrolled:

Table 4

	American Indian or Alaskan Native	Asian or Pacific Islander	Black, not of Hispanic Origin	Hispanic	White, not of Hispanic Origin	Other or Unknown	Total
Female	0	1	1	0	3		5
Male	1	0	0	1	3		5
Total	1	1	1	1	6		10

7. Data Management

[name] and [name] currently speak about weekly and will continue to do so. They will review data together every month for this small pilot trial by 1) Reviewing and analyzing the progress of the study; 2) Monitoring the safety of the study treatments and diagnostic procedures; 3) Ensuring data quality; 4) Reviewing interim analyses and recommending early stopping or continuation of the trial (if applicable); and 5) Reviewing recruitment and event rates.

The trial PIs and clinical coordinators will review the study progress weekly. Patients entered on the trial and adverse events will be reviewed to ensure that the study is implemented as outlined in the protocol. Data will be collected on case report forms, which will be uploaded to the DMCC. All study data will be collected via systems created in collaboration with the RDCRN Data Management and Coordinating Center and will comply with all applicable guidelines regarding patient confidentiality and data integrity. Each site will have internal reviews carried out quarterly by clinical trials specialists to ensure that all protocol specifications are being followed and issues addressed promptly. Quarterly reports will be generated by KKI to assess completeness of data. There will be monthly phone conferences between KKI and CCHMC to address quality assurance (QA) issues. De-identified blood samples will be run at each site separately and the results will be sent from the KKI to CCHMC for PK testing. Dose adjustments for all patients in the study will be decided based on the PK testing performed at CCHMC.

The Principal Investigator at each site will review all data relating to safety and tolerability throughout the pilot study. Any subject experiencing significant side effects or medical concerns during the course of study treatment will be responded to appropriately as clinically warranted or as outlined in this protocol by [name] and [name]. If the subject is not doing well clinically and the patient, parent, [name] or [name] thinks that it is in the best interest of the subject to stop the study drug, then they will be removed from the pilot study. If the subject meets any of the early stopping requirements then they will be removed from the study. Internal monitoring of scientific data collection and quality of research will occur at both sites.

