The quantification of the facial birthmark score developed and validated at the KKI will occur at the beginning of the study, prior to starting study drug, and when the subjects reach the endpoint of the study at six months' time while still on study drug (Waelchli et al., 2014). If the subject elects to enter the Extension Phase, the facial birthmark will be rated at each Extension Phase visit. Descriptive statistics for this measure will be reported in the form of median and range. Mann Whitney U Test will be used to assess whether a significant change in the facial birthmark has occurred after treatment compared to prior to treatment. Facial birthmark scoring will occur at both sites, KKI and CCHMC, and the de-identified results will be sent to KKI for analysis.

Biomarker Development: Spearman's rho will be used to assess for the strength, direction and significance of correlations between qEEG results and neuropsychological outcomes, NeuroQoL and the SWS Neuroscore. Significance will be taken at p<0.05.

All of these outcomes will be used to determine whether sirolimus is 1) sufficiently well tolerated in this small group of subject and 2) what outcome measures and biomarkers demonstrate preliminary evidence of being responsive to sirolimus. This information will be used to determine the advisability of proceeding with a larger multicentered study and aid in the selection of outcome measures and biomarkers to be part of that follow-up randomized placebo-controlled trial.

Sponsors (federal, state, foundation and industry support): National Institute of Health (NIH) Faneca 66 Foundation

Pfizer (study drug only)

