5.2 Definitions and Standards

The Rare Diseases Clinical Research Network defines an adverse event as: "...an unfavorable and unintended sign, symptom or disease associated with a participant's participation in a Rare Diseases Clinical Research Network study."

Serious adverse events include those events that: "result in death; are life-threatening; require inpatient hospitalization or prolongation of existing hospitalization; create persistent or significant disability/incapacity, or a congenital anomaly/birth defects."

An unexpected adverse event is defined as any adverse experience...the specificity or severity of which is not consistent with the risks of information described in the protocol.

Expected adverse events are those that are identified in the research protocol as having been previously associated with or having the potential to arise as a consequence of participation in the study

All reported adverse events will be classified using the current version of the Common Terminology Criteria for Adverse Events (CTCAE) Version 4.0 developed and maintained by CTEP at National Cancer Institute.

Prior to the use of this drug, patients and/or their parents/guardian will be advised of the possibility of untoward symptoms. These adverse reactions are not expected at the low doses being used in this pilot study.

5.3 Expected/Known Risks/Discomforts/Adverse Events Associated with Study Intervention and Procedures: Definition of Expected Adverse Events

The primary risk to the subjects from participation in this trial is from sirolimus. From prior studies, it is already known that in this dose range the risks of Serious Adverse Events due to sirolimus is very low, hence why this dose range was picked. The tables below have published adverse events for a much higher dose range. We do not expect any Serious Adverse Events. The occurrence of any Serious Adverse Event thought to be due to the study drug will trigger a review to consider a change in study protocol or stopping the trial. The risk of low-dose sirolimus, specifically in patients with Sturge-

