5.5 RDCRN Adverse Event Data Management System (AEDAMS)

Upon entry of a serious adverse event, the DMCC created Adverse Event Data Management System (AEDAMS) will immediately notify the Study Chair, site PIs, the Medical Review Officer, and any additional agencies (if applicable- industry sponsor, CTEP, etc) of any reported adverse events via email.

Serious adverse events: The NIH appointed Medical Review Officer (MRO) determines causality (definitely not related, probably not related, possibly related, probably related, definitely related) of the adverse event. The MRO may request further information if necessary and possibly request changes to the protocol or consent form as a consequence of the adverse event. A back-up notification system is in place so that any delays in review by the MRO beyond a specified period of time are forwarded to a secondary reviewer. The Adverse Event Data Management System (AEDAMS) maintains audit trails and stores data (and data updated) and communication related to any adverse event in the study.

Non-serious expected adverse events: Except those listed above as immediately reportable, non-serious expected adverse events that are reported to or observed by the investigator or a member of his/her research team will be submitted to the DMCC in a timely fashion (within 20 working days). The events will be presented in tabular form and given to the MRO on a bi-annual basis. Local site investigators are also required to fulfill all reporting requirements of their local institutions.

The DMCC will post aggregate reports of all reported adverse events for site investigators and IRBs.

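### The safety condition for planning the follow-up trial leaves out SAEs definitely related to sirolimus: probably a drafting slip, and one word mends it

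*Combined protocol and SAP*

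**What the plan says.** Section 6 (Statistical Considerations) states when the pilot will lead to a larger study. The safety part reads "If no serious adverse events which are thought to probably or possibly be due to the study drug". The sentence continues "AND the cognitive data suggests a trend for possible benefit, then the results of this study will be used to plan a larger follow-up clinical", where the noun cut off is trial. Both parts must hold. The sentence does not say who does the thinking about causality, or which subjects are counted.

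Section 5.5 gives SAE causality to the NIH-appointed Medical Review Officer, on the scale "definitely not related, probably not related, possibly related, probably related, definitely related".

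Section 5.3 refers to drug-related toxicity twice in terms of that scale. The drug-hold rule begins "Any patient experiencing a Grade 3 or 4 toxicity that is possibly, probably, or definitely related to sirolimus", and the removal list is headed "Sirolimus-related (possibly, probably, or definitely) toxicities Requiring Dose Interruptions or other interventions and removal from study". Both name all three related levels.

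On who counts, the Synopsis sets the sample size at 10 and leaves out of that number those who withdraw within the first two months on drug. Section 5.7 says such subjects are replaced. It also keeps data collected before termination in the primary analysis unless consent is withdrawn.

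**The concern.** A condition for moving to a larger trial should cover the strongest causal grade at least as firmly as the weaker ones. On its words, Section 6 does the reverse: one possibly related SAE fails the safety part, and one definitely related SAE does not. The protocol has a graded scale on which that difference can be recorded, and elsewhere it uses all three related grades, so the wording is inconsistent with the rest of the document.

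Two smaller gaps sit beside it. Because no assessor is named, the site's view and the Medical Review Officer's grade could differ with no rule for which one governs. Because no denominator is named, a subject who has a related SAE early, leaves and is replaced could fall outside the nominal 10. Section 5.3 makes that sequence possible, since it removes subjects for related Grade 3 or 4 toxicity, with listed exceptions.

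**Working it through.** The plan gives no figure to reproduce. Section 6 bases the 10 subjects on availability and experience, not on a calculation. The check is a comparison of texts.

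**Step 1. Map the Section 5.5 scale onto the Section 6 safety part.**

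| Causality grade (Section 5.5) | Fails the safety part as written? | Fails it with the third level added? |
|---|---|---|
| Definitely not related | No | No |
| Probably not related | No | No |
| Possibly related | Yes | Yes |
| Probably related | Yes | Yes |
| Definitely related | **No** | Yes |

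As written, 2 of the 3 related grades fail the condition. With one word added, all 3 do.

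**Step 2. Look for text that closes the gap.**
- Section 5.3: "The occurrence of any Serious Adverse Event thought to be due to the study drug will trigger a review to consider a change in study"; the change is to the protocol, and halting the trial is named as the alternative. This covers a definitely related SAE, but it concerns the present trial.
- Section 5.0: an SAE directly attributable to the drug leads to a review of whether that participant continues. This concerns the participant.
- Synopsis, statistical considerations: after asking whether tolerability is sufficient, it says "This information will be used to determine the advisability of proceeding with a larger multicentered study". This concerns progression but sets no SAE criterion.

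None of these adds the missing level to Section 6.

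**Step 3. When could the omission matter?** Only if at least one SAE is graded definitely related, none is graded possibly or probably related, and the clause is applied to the letter. The documents give no rate for such events, so any rate is an assumption. The chance of at least one affected subject among 10 is 1 − (1 − p)^10:
- p = 1%: 1 − 0.99^10 = 9.6%
- p = 2%: 1 − 0.98^10 = 18.3%
- p = 5%: 1 − 0.95^10 = 40.1%
- p = 10%: 1 − 0.90^10 = 65.1%

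For 10 dosed subjects at each assumed rate, these are ceilings on how often the gap could come into play, because the other two requirements must also hold.

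**Step 4. Optional reporting: what zero events would show.** With 0 of n affected, the exact 95% upper bound is 1 − 0.05^(1/n) one-sided and 1 − 0.025^(1/n) two-sided. For n = 10 these are 1 − 0.05^(0.1) = 0.259 and 1 − 0.025^(0.1) = 0.308, or about 26% and 31%. These figures are the same whether or not the wording is corrected, so they do not measure the omission. If replaced subjects are counted, n may exceed 10 and the bounds would be somewhat lower.

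**The case against.** The strongest reply is that the sentence is plain prose and sets a floor. Anyone who requires no possibly related SAE also means to require no definitely related one. The Section 5.3 review trigger, which takes in any SAE attributed to the drug, and the three-level wording in the same section point to that intent. Section 5.3 governs drug holds and removal, a different decision, so the mismatch looks more like loose wording than a disagreement of substance. All of this stands, and it is why the practical risk is low.

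A reader might go further and infer that the plan lets the worst safety finding through to a larger trial. The documents do not support that, for three reasons.
- The sentence says when the results will be used for planning. It does not say what happens otherwise, so strictly no grade of SAE blocks progression under it.
- Section 6 does not cite the Section 5.5 scale or say that the condition is a filter on coded grades. Applying it that way is an inference.
- Section 6 plans a follow-up only if one is warranted, Section 2 only if this trial justifies it, and the Synopsis leaves an overall judgment of advisability. NIH, the FDA and the local IRBs can also stop the pilot under Section 5.6.

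Nor does the plan call zero events proof of safety. It claims only a preliminary understanding, and it requires a cognitive trend as well. The follow-up should not be described as a trial in children either: the pilot enrols ages 3 to 31, and no age range is given for the next trial.

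What survives is the text itself. The level is missing and nothing else supplies it in Section 6.

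**Conclusion.** The point holds, as a minor one. Read literally against the protocol's own causality scale, the safety condition in Section 6 omits one of three related levels, the strongest, so a definitely related SAE would still meet it. This is probably a drafting slip, and investigators would be unlikely to proceed because of it. It merits correction because it lies in the only progression condition specific to SAEs, and a reader should not have to supply its most serious category.

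The literal result assumes that the condition is read with the Section 5.5 grades, which is natural but not stated. The unnamed assessor and the unstated denominator are gaps in the same sentence and can be closed with it. The upper bounds for 0 of 10 are a reporting suggestion and no part of the error.

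**What to change.** In Section 6, replace the two-level wording with the phrase that Section 5.3 already uses: "possibly, probably, or definitely related to sirolimus". Add one sentence saying that the condition uses the Medical Review Officer's classification under Section 5.5, and that it counts every subject who received study drug, including those who withdraw within the first two months and are replaced.

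Optionally, report the number of dosed subjects with a related SAE, and the exact 95% upper bound based on the actual number dosed, beside the decision on the follow-up trial.

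The cost is one added word, one sentence and, if wanted, one interval. No new data, visits or subjects are needed, and no rule for managing patients changes.
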